10.1 Protocol Specific Reporting for Serious Adverse Events (SAEs)

DEFINITION: ICH Guideline E2A and Fed. Reg. 62, Oct. 7, 1997 define serious adverse events as those events which meet any of the following criteria?

- Results in death

- Is life threatening (Note: the term life-threatening refers to an event in which the patient was at risk of death at the time of the event; it does not refer to an event which hypothetically might have caused death if it were more severe).
- Requires inpatient hospitalization or prolongation of existing hospitalization
- Results in persistent or significant incapacity or substantial disruption of the ability to conduct normal life functions.
- Is a congenital abnormality/birth defect
- Events that may not meet these criteria, but which the investigator finds very unusual and/or potentially serious, will also be reported in the same manner.
- **Grades 4 and 5 expected (solicited) and unexpected (unsolicited) SAEs that meet the above definition for SAEs and/or regardless of attribution (i.e. regardless of whether they are related to this study intervention or not) should be reported to the RB DMC using the FDA Form 3500 (MedWatch).**
- Site staff and/or Principal Investigators will report to the RB Data Management Staff within 24 hours of discovering the details of all unexpected severe, life-threatening (grade 4) and/or fatal adverse events (grade 5) if there is reasonable suspicion that the event was definitely, probably, or possibly related to the study intervention.

Otherwise, the MedWatch should be sent to the RB DMC by fax or email within 10 working days of discovering the details of the SAE.

Data Elements to include on the MedWatch are:

- SAE reported date
- CTCAE Term (v4.03)
- Event onset date and event ended date
- Severity grade (use table provided in Section 10.1.3 below)
- Attribution to study intervention (relatedness)
- Action taken with the study participant and intervention
- Outcome of the event
- Comments

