10. REPORTING ADVERSE EVENTS

- A list of serious adverse events that have occurred or might occur that are related to this study intervention can be found in Section 6.2.
- Serious Adverse Event reporting begins after the informed consent is signed.
- Serious Adverse Events occurring within 30 days of study completion must be reported via FDA Form 3500 (MedWatch).

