10.2 Guidelines to determine grade and severity of AEs and/or SAEs

Identify the adverse event using the NCI Common Terminology Criteria for Adverse Events (CTCAE) version 4.03. The CTCAE provides descriptive terminology and a grading scale for each adverse event listed. A copy of the CTCAE can be found at http://ctep.cancer.gov/protocolDevelopment/electronic_applications/ctc.htm#ctc_40

AEs will be assessed according to the CTCAE grade associated with the AE term. AEs that do not have a corresponding CTCAE term will be assessed according to the general guidelines for grading used in the CTCAE v4.03. as stated below.

Grade	Severity	Description
1	Mild	Mild; asymptomatic or mild symptoms; clinical or diagnostic observations only; intervention not indicated.
2	Moderate	Moderate; minimal, local or noninvasive intervention indicated; limiting age-appropriate instrumental ADL*.
3	Severe	Severe or medically significant but not immediately life-threatening; Hospitalization or prolongation of hospitalization indicated; disabling; limiting self-care ADL**.

4	Life threatening	Life-threatening consequences; urgent intervention indicated.
5	Fatal	Death related to AE.

Activities of Daily Living (ADL)

- * Instrumental ADL refer to preparing meals, shopping for groceries or clothes, using the telephone, managing money, etc.
- ** Self-care ADL refer to bathing, dressing and undressing, feeding self, using the toilet, taking medications, and not bedridden.

The Research Base Grant PI, Safety and Toxicity Review Committee and/or Study Chair will take appropriate action to inform the membership and statistical personnel of any protocol modifications and/or precautionary measures, if this is warranted.

The RB DMC is responsible for communicating AEs/SAEs to the FDA, the drug sponsor, WF IRB, the WF Safety and Toxicity Review Committee (STRC) and/or other regulatory agencies as appropriate per agency reporting requirements.

Institutions must comply with their individual Institutional Review Board (IRB) policy regarding submission of documentation of adverse events. All MedWatch reports should be sent to the local IRB in accordance with the local IRB policies.

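### Section 10 contradicts itself on which serious adverse events need a MedWatch report: the definition has no grade limit, but the general reporting and follow-up rules cover only Grades 4 and 5

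*Combined protocol and SAP*

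**What the plan says.** Section 10.1 lists the criteria that make an event serious. Two matter here: "Requires inpatient hospitalization or prolongation of existing hospitalization" and "Results in persistent or significant incapacity or substantial disruption of the ability to conduct normal life functions". Neither carries a grade limit.

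The same section then says, in bold, what must go on FDA Form 3500 (MedWatch) to the Research Base Data Management Center (RB DMC): "Grades 4 and 5 expected (solicited) and unexpected (unsolicited) SAEs that meet the above definition for SAEs", with or without a link to the intervention. A separate 24-hour duty applies to "all unexpected severe, life-threatening (grade 4) and/or fatal adverse events (grade 5" where a link to the intervention is at least possible. The default time limit follows: "Otherwise, the MedWatch should be sent to the RB DMC by fax or email within 10 working days".

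The general grading table in Section 10.2 labels Grade 3 as Severe and describes it in part as "Hospitalization or prolongation of hospitalization indicated; disabling; limiting self-care ADL". Section 10.3 confines follow-up to related serious events of Grade 4 or 5. The opening of Section 10 has no such limit: "Serious Adverse Events occurring within 30 days of study completion must be reported via FDA Form 3500 (MedWatch".

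**The concern.** The definition works by outcome (admission, incapacity, death), whereas the general reporting rule adds a threshold on severity grade. Where the two disagree, a site has no single answer to whether a report is due. The protocol's own table puts admission and disability at Grade 3, one step below the threshold, so the disagreement falls on a common kind of serious event and not on a rare corner case.

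What is at stake is the prompt route. Under Section 10.2 the RB DMC passes adverse events to the FDA, the drug sponsor, the institutional review board and the Safety and Toxicity Review Committee, and MedWatch forms also go to local review boards. Under Section 10.4 new MedWatch reports are circulated to sites each month. Section 12.10 has the monitoring committee look at serious-event incidence every six months. If sites read the duty differently, prompt notice is patchy and that incidence depends partly on each site's reading.

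**Working it through.** The plan states no figure on this point and gives no event rates, so there is no arithmetic. The check is to take each rule's scope and ask whether it obliges a MedWatch report.

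**Scope of each rule**

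- Definition of serious (10.1): any grade that meets a criterion.
- General MedWatch rule (10.1): Grades 4 and 5, expected or unexpected, related or not.
- 24-hour rule (10.1): unexpected and at least possibly related. It names Grades 4 and 5 and also uses the word *severe* with no grade attached.
- Default time limit (10.1): 10 working days. It sets timing and does not say that other grades are covered.
- Completion rule (opening of 10): any grade, tied to the 30 days around study completion.
- Catch-all (10.1): events outside the criteria that the investigator finds very unusual or potentially serious; discretionary.
- Follow-up rule (10.3): Grades 4 and 5, related.

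**Applying them to events that meet the definition**

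| Serious event | General rule | 24-hour rule | Completion rule | MedWatch clearly required? |
|---|---|---|---|---|
| Grade 4 or 5, any time | Yes | If unexpected and related | If in window | Yes |
| Grade 3, within 30 days of completion | No | Depends on *severe* | Yes | Yes |
| Grade 3, during treatment, unexpected, related | No | Depends on *severe* | No | Unclear |
| Grade 3, during treatment, expected, related | No | No (expected) | No | No |
| Grade 3, during treatment, unrelated | No | No (unrelated) | No | No |

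Two things follow. First, the same Grade 3 event needs a form if it falls near completion but not, on a literal reading, if it falls mid-treatment. Second, the row with no cover on any reading of the 24-hour rule, and the most relevant to the drug, is the expected related event. Section 6.2 lists rare but serious statin events: cholestatic hepatitis, rhabdomyolysis, compartment syndrome and tendon rupture. A case that led to admission without being life-threatening would fall in that row if it were graded 3. That grading is an assumption, because the CTCAE term definitions are not in the documents.

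The grade limit is stated in both 10.1 and 10.3, so it is not a single slip of the pen.

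**The case against.** The strongest reply is that this is loose drafting and not a rule that excludes a class of events. *Severe* is the table's own label for Grade 3, so the 24-hour rule can naturally be read to include unexpected related Grade 3 events. The opening of Section 10 starts serious-event reporting at consent with no grade limit. The catch-all says that other worrying events are reported as well, which presupposes that events meeting the criteria are reported. The bolded sentence is itself garbled where it turns to attribution. All of this stands as evidence of ambiguity. None of it settles the scope, and none brings expected related Grade 3 events during treatment within a stated duty.

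A reader might infer that drug-related hospitalisations go unreported or are missing from board review. The documents do not support that. Toxicities are assessed by telephone at 12 and 18 months (7.1, 7.3), completion includes structured interviews on adverse events (7.4), and a contact follows 30 days after the last dose (7.5). Board reports list toxicities and adverse events with relationship and arm (11.4), and interim reviews cover adverse events as well as serious ones (12.10). The form appendices are not shown, so a gap in routine capture cannot be claimed. These routes do follow scheduled assessments, which are six months apart after month 6, so they do not replace prompt reporting.

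A reader might also infer that every serious event graded 3 is affected. The completion rule covers some, and the 24-hour rule may cover others. Section 10.2 also applies its general table only to events without their own CTCAE term, so not every admission will be Grade 3. The mismatch itself does not depend on the table: the definition has no grade limit and the general rule has one.

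Finally, the threshold may be deliberate, to limit reports of chemotherapy admissions. That would be a reasonable aim, but the protocol does not state it and the completion rule runs against it.

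**Conclusion.** The contradiction is in the text and should be resolved. As written, a Grade 3 serious event during treatment is not clearly required to reach the RB DMC on a MedWatch form. For an expected event related to study drug, no reading of the 24-hour rule closes the gap.

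The consequence is uneven or delayed serious-event reporting, not certain loss. Because treatment is blinded, differing site practice would not by itself favour an arm; it would thin the counts on which a safety difference has to be seen. There is no bearing on the LVEF analysis. The size cannot be computed from the documents.

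The conclusion rests on reading the bolded sentence in Section 10.1 literally and on some qualifying events being graded 3.

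**What to change.** Reconcile the opening of Section 10 with Sections 10.1 and 10.3, so that the scope of reporting and follow-up matches the protocol's own definition of serious.

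- At minimum, state that Grade 3 serious events judged at least possibly related to study drug are reported and followed, whether expected or not. This uses attribution categories already in Section 10.1 and leaves out unrelated chemotherapy admissions.
- Say whether *severe* in the 24-hour rule means Grade 3.
- If a grade threshold is intended for unrelated events, say so, give the reason, and make the completion-window sentence agree with it.
- Correct the pointer in Section 10.1 to a severity table in Section 10.1.3; the table is in Section 10.2.

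The cost is a wording amendment and, with the minimum option, what should be a small number of extra site reports.

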10.2 Guidelines to determine grade and severity of AEs and/or SAEs

Identify the adverse event using the NCI Common Terminology Criteria for Adverse Events (CTCAE) version 4.03. The CTCAE provides descriptive terminology and a grading scale for each adverse event listed. A copy of the CTCAE can be found at http://ctep.cancer.gov/protocolDevelopment/electronic_applications/ctc.htm#ctc_40

AEs will be assessed according to the CTCAE grade associated with the AE term. AEs that do not have a corresponding CTCAE term will be assessed according to the general guidelines for grading used in the CTCAE v4.03. as stated below.

Grade	Severity	Description
1	Mild	Mild; asymptomatic or mild symptoms; clinical or diagnostic observations only; intervention not indicated.
2	Moderate	Moderate; minimal, local or noninvasive intervention indicated; limiting age-appropriate instrumental ADL*.
3	Severe	Severe or medically significant but not immediately life-threatening; Hospitalization or prolongation of hospitalization indicated; disabling; limiting self-care ADL**.

4	Life threatening	Life-threatening consequences; urgent intervention indicated.
5	Fatal	Death related to AE.

Activities of Daily Living (ADL)

- * Instrumental ADL refer to preparing meals, shopping for groceries or clothes, using the telephone, managing money, etc.
- ** Self-care ADL refer to bathing, dressing and undressing, feeding self, using the toilet, taking medications, and not bedridden.

The Research Base Grant PI, Safety and Toxicity Review Committee and/or Study Chair will take appropriate action to inform the membership and statistical personnel of any protocol modifications and/or precautionary measures, if this is warranted.

The RB DMC is responsible for communicating AEs/SAEs to the FDA, the drug sponsor, WF IRB, the WF Safety and Toxicity Review Committee (STRC) and/or other regulatory agencies as appropriate per agency reporting requirements.

Institutions must comply with their individual Institutional Review Board (IRB) policy regarding submission of documentation of adverse events. All MedWatch reports should be sent to the local IRB in accordance with the local IRB policies.

10.3 Follow-up of SAEs

Site staff should send follow-up reports as requested when additional information is available. Additional information should be entered on the MedWatch form in the appropriate format. Follow-up information should be sent to the RB Data Management Center as soon as available.

SAEs (Grade 4 and/or Grade 5) for this protocol should be followed for those related to the study intervention. Documentation should include:

- PID
- Date of SAE
- Description of the event
- Relationship of the SAE to the study intervention
- Severity
- Intervention/Resolution

10.4 Adverse Event Posting

Adverse event summaries are posted on the WF RB website each month. New MedWatches are emailed to sites the 1st week of each month and posted on the password protected CCRBIS.

11. STUDY MONITORING

11.1 Data Management Schedule

The Eligibility checklist/Enrollment Form should be completed on-line prior to placing the patient on study. Data forms will be submitted to the WF NCORP Research Base. See Section 6.8.2 for mailing address, or fax to [contact] according to the timetable below:

Form	Submission Schedule
Consent Form, MRI Encounter Form, Baseline Neurocognitive Booklet, Flow Sheet/Addenda, Current Medication Form	Baseline within 14 days of enrollment
MRI Encounter Form, 6 month Neurocognitive Booklet, Flow Sheet/Addenda, Current Medication Form	6 months within 14 days of assessment
Flow Sheet/Addenda	1 and 3 months within 14 days of assessment
Radiation Treatment Form	Complete within 14 days of pt. receiving last RT tx. or indicating patient will not receive RT.
12 month Neurocognitive Booklet, Flow Sheet/Addenda, Telephone Contact Form, Current Medication Form	12 months within 14 days of assessment
18 month Neurocognitive Booklet, Flow Sheet/Addenda, Telephone Contact, Current Medication Form	18 months within 14 days of assessment
MRI Encounter Form, 24 month Neurocognitive Booklet, Flow Sheet/Addenda, Current Medication Form	24 months within 14 days of assessment
Medication Diaries	Every other month within 14 days of completion
Early Withdrawal Form	Participants who withdraw from treatment or study prior to completion. Submit within 14 days of withdrawal.
Open Label Form (See page 2 Physician Update)	If placed on a statin by their physician within 14 days of occurrence.
Chemotherapy Treatment Form	Within 14 days of completion. of each course (not cycle)
Screening Form	Every month within 14 days of completion
1 Month Post Final Assessment Contact Form (For patients completing at least 24 months of study medication but no more than 27 months)	Complete this form 30 days after last dose of study medication. Submit within 14 days of assessment.

11.2 Case Report Forms

Participant data will be collected using protocol-specific case report forms (CRF).

11.3 Source Documents

Source documents are the original signed and dated records of participant information (e.g., the medical record, shadow chart) which may include electronic documents containing all the information related to a participant's protocol participation. Source documents are used to verify the integrity of the study data, to verify participant eligibility, and to verify that mandatory protocol procedures were followed. An investigator and other designated staff are required to prepare and maintain adequate and accurate documentation that records all observations and other data pertinent to the investigation for each individual participating in the study. All data recorded in the research record (including data recorded on CRFs) must originate in the participant's medical record, study record, or other official document sources.

Source documents substantiate CRF information. All participant case records (e.g., flow sheets, clinical records, physician notes, correspondence) must adhere to the following standards:

- Clearly labeled in accordance with HIPAA practices so that they can be associated with a particular participant or PID;
- Legibly written in ink;
- Signed and dated in a real time basis by health care practitioner evaluating or treating the participant;
- Correction liquid or tape must not be used in source documents or on CRFs.
- Corrections are made by drawing a single line through the error. Do not obliterate the original entry. Insert the correct information, initial, and date the entry.

All laboratory reports and imaging study and scans must have:

- Complete identifying information (name and address of the organization performing, analyzing, and/or reporting the results of the test); and
- Range of normal values for each result listed.

11.4 Data and Safety Monitoring Board

The Data Safety Monitoring Board meets every six months to review all phase II and phase III protocols. The Board includes members demonstrating experience and expertise in oncology, biological sciences, biostatistics and ethics. The DSMB report is generated by the RB statistician. Areas of review may include the following: Date study Opened; Study Objectives; Patient Accrual; Patient Status and Retention; Study Status; Last Contact Status; Patient Compliance; Number of Biopsies/Labs as needed; Patient Characteristics; Summary of Observed Toxicities; Adverse Events; Date, Event briefly described, Relationship to Drug, Arm assigned; Summary of Primary and Secondary Measures. Following each meeting, WF RB will provide DSMB reports to all accruing sites via the regular weekly email correspondence.

11.5 Record retention

Clinical records for all participants, including CRFs, all source documentation (containing evidence to study eligibility, history and physical findings, laboratory data, results of consultations, etc.), as well as IRB records and other regulatory documentation will be retained by the Investigator in a secure storage facility in compliance with HIPAA, OHRP, FDA regulations and guidance, and NCI/DCP requirements unless the standard at the site is more stringent.

11.6 CDUS Reporting

The WF NCORP Research Base Data Management Center will submit quarterly reports to DCP/CTEP by electronic means using the Clinical Data Update System (CDUS)

12. STATISTICAL CONSIDERATIONS

12.1. Study Design/Endpoints

This is a multi-center, double-blind, placebo-controlled clinical trial that randomizes 278 participants into 1 of 2 treatment arms: Group 1 (one 40 mg atorvastatin tablet each morning by mouth for 24 months) or Group 2 (one placebo tablet each morning by mouth for at least 24 months but no more than 27 months) with the goal of having at least 200 remaining at the trial's end for final assessments (assuming an approximate 28% loss to follow-up). A permuted block randomization stratified by cancer type (breast vs lymphoma) and **planned** Anthracycline-based therapy doses of Doxorubicin < or ≥ 240 mg/m² or Epirubicin < or ≥ 400 mg/ m²; close to the median dose of our pilot studies) will ensure treatment group balance is achieved within strata. As in all our pilot studies and clinical practice, Doxorubicin and Epirubicin doses will be assessed to account for receipt of different anthracyclines. The primary endpoint in this trial is LVEF, and thus the primary efficacy analysis will examine whether the statin therapy can attenuate the reduction in LVEF in patients with breast cancer or lymphoma who receive Anthracycline-based therapy. Primary endpoints include LVESV, LV end diastolic volume (LVEDV), LV mid-wall circumferential strain, T1-ECV (a measure of replacement fibrosis), PWV, aortic wall thickness, CRP and TNF- α , serum lipoprotein levels, and circulating neurohormones.

12.2. Primary Aims

Specific Aim 1: To determine if atorvastatin administration preserves LVEF 24 – 27 months after receipt of Anthracycline-based therapy for breast cancer and lymphoma.

Specific Aim 2: To determine if baseline to 6-month differences in LVEF predict baseline to 24- 27 month differences in LVEF after Anthracycline-based therapy and concomitant atorvastatin therapy.

12.3. Analysis Plan

The primary hypothesis for Specific Aim 1 is that statin use will protect against a harmful reduction in LVEF measured over 24 – 27 months for patients with breast cancer or lymphoma who receive Anthracycline-based therapy. All randomized patients will be used in the analysis to compare groups (“intent to treat” approach). Since LVEF is measured on a continuous scale and this is a randomized trial, our primary analysis will fit an analysis of covariance (ANCOVA) model that compares the 24- 27 month values of LVEF between groups adjusting for the baseline (pre-treatment) levels of LVEF and stratification factors. Note that patients are stratified by planned dose and that is the stratification that will be used in the analysis, even if the patient ends up getting a different dose. This analysis will address the first specific aim.

To address the second primary aim, we will examine whether the early treatment effect of statin use (6 months post randomization) predicts the long-term (24 – 27 month) effect of statins. Pilot data (Section 2) suggest that Anthracycline-based therapy injury occurs early and concomitant statin use attenuates this early Anthracycline-based therapy-mediated injury. We will fit an ANCOVA model that compares the 24- 27 month LVEF values for the treated and control groups and will also include covariates for the baseline LVEF and 6-month change in LVEF values. We will examine the treatment by 6-month LVEF change interaction to determine whether the correlation between early and late changes in LVEF differs by treatment. Thus, this model will have 4 terms of interest: the main effect for treatment, the main effect for the change in LVEF after 6 months, the main effect for baseline pre-treatment LVEF, and the treatment by change in LVEF after 6-month interaction. If the interaction is non-significant, we will examine the model with the 3 main effects. Since there may be limited power to test this interaction, we will use a 0.15 threshold for testing significance of the

interaction term in the model.

After primary efficacy analyses, additional analyses of the primary hypotheses will be done to assess relationships between treatment and outcome. We will fit ANCOVA models that consider the 24-27 month LVEF measure as the outcome, the baseline LVEF measure as a covariate, and other patient-level characteristics (e.g. age, cancer type, stage, and race) in order to control for other baseline covariates possibly related to LVEF in the model. Interactions between the treatment and covariates will be examined to determine whether the treatment effect is consistent across subgroups (e.g., black/white race by treatment interaction). Finally, we will conduct a repeated measures ANCOVA model that incorporates the intermediate (6-month) LVEF measurement into the model. We anticipate examining different covariance structures. Past experience suggests that a compound symmetry structure is usually appropriate; we will also examine whether an unstructured covariance is needed. We will fit these models using a mixed models approach, where the individual patient will be treated as a random effect in the model and the treatment indicator as patient characteristics (and baseline LVEF) will be considered as fixed effects. A mixed models approach for modeling the longitudinal data will allow for appropriate inference to be made in the presence of missing data (i.e., patient drop-outs) if the missing data are missing at random (MAR). Below, we describe methods to address MAR assumptions. Diagnostics and residual plots will be reviewed to ensure that all assumptions are met. If not, transformations of the outcome data will be considered, where the order of the priority in choosing a transformation will be to satisfy the (1) linearity assumption, (2) homogeneity assumption (homoscedasticity), and (3) normality assumption.

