12.4. Potential Analytic Concerns in Primary Efficacy Analyses

Lost to Follow-up: We designed this study to recruit 278 total patients so that 200 are available at the end of the study. Thus, we will need to consider how to analyze data from the 78 patients who may drop out. To examine whether the missing data are either missing completely at random or missing at random, we will compare the baseline characteristics of those who drop out and those who complete the trial. If there is no evidence of informative missing data, analyses will be done using the repeated measures ANCOVA with a mixed models approach (PROC MIXED in SAS). However, if there is evidence that the missing data are informative and treatment-related (e.g. if there are fewer dropouts in the statin group or if missingness is related to other medical outcomes that are strongly associated with the outcome of interest) and not MAR, then we will use more sophisticated statistical methods.⁷⁸⁻⁸⁰ One possible approach is to model the probability of dropping-out for each participant conditional on their baseline characteristics and treatment assignment. These probabilities would then be used to stratify participants (both completers and drop-outs) before making treatment comparisons. Thus each stratum would contain participants with similar predicted probabilities of trial completion (although only a subset would be completers). The final treatment effect estimates could be made using the completers with weights assigned to them based on the ratio of drop-outs to completers within each stratum. This approach and other methods for handling missing data have been previously described by [name].⁷⁸⁻⁸⁰

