In the above, r^2 is the percent of the variance of the follow-up outcome explained by the baseline measurement (LVEF), $Z_{1-\alpha/2}$ is the value from the standard normal distribution corresponding to the alpha level chosen (1.96, which corresponds to alpha=0.05 [two sided]), $Z_{1-\beta}$ is the value from the standard normal distribution that corresponds to the power chosen for the study (here 80% and 90%), and $n=100$ corresponds to the total number of patients studied for the statin group. We chose this sample size (100 per group) for power calculations to allow for up to 78 patients out of the 278 accrued to potentially drop-out. Note that this will somewhat conservative for the mixed models as those with partial data will also provide information. Based on preliminary data examining LVEF levels in comparable patients measured over a 6-month period we found that the standard deviation was approximately 7.7 and the correlation between baseline and 6-months was 0.5. Since we do not know what the correlation will be after 2 years, Table 5 depicts detectable differences for different correlations and power values. In addition, we show detectable differences for key secondary variables for which we have preliminary data (LVEDV, LVESV, and PWV).

Thus, for example, we have 80% power to detect a difference of 2.6% in LVEF between groups if the correlation between the baseline and 24-month LVEF is 0.5. In preliminary observational data, we saw a difference in LVEF between statin users vs. those who were not of 2.5% at 6 months. Thus, effect sizes of the magnitude in Table 5 are plausible and clinically meaningful. 2-6 ml increases in LVESV, or 3-5% drops in LVEF (from a normal resting LVEF) have been associated with adverse CV prognoses in a recent large trial of patients with HF and a preserved resting LVEF.⁸¹ In 483 hypertensive patients aged 50±13 years, aortic PWV measures of 11 m/s were associated with odds ratio of 2.14 for cardiac events ($p<0.0001$).⁸² Other studies that have initiated generic therapies such as ACE inhibitors or beta blockers with antioxidant properties have shown a reduced occurrence of CV events in cancer survivors.⁸³ Importantly however, it remains to be seen whether early initiation of statin therapy reduces the onset of subclinical CV disease in patients with breast cancer or lymphoma.

Outcome	Estimated SD	80% Power			90% Power		
		Correlation between baseline and 2-yr measure					
		0.4	0.5	0.6	0.4	0.5	0.6

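### The repeated-measures model that section 12.4 brings in under dropout has no specified visit term, treatment-by-visit term or 24–27 month contrast; fitted as listed, it averages the 6- and 24-month effects

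*Combined protocol and SAP*

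**What the plan says.** Section 12.2 states Aim 1 as "To determine if atorvastatin administration preserves LVEF 24 – 27 months after receipt of Anthracycline-based therapy". The primary analysis in section 12.3 is a single-time ANCOVA that "compares the 24- 27 month values of LVEF between groups adjusting for the baseline (pre-treatment) levels of LVEF and stratification factors", and the section says that this analysis addresses Aim 1.

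Further on, among analyses to follow the primary ones, section 12.3 adds "a repeated measures ANCOVA model that incorporates the intermediate (6-month) LVEF measurement into the model". Patient is a random effect, and "the treatment indicator as patient characteristics (and baseline LVEF) will be considered as fixed effects". On covariance it says "Past experience suggests that a compound symmetry structure is usually appropriate", and that an unstructured form will also be examined.

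Section 12.4, whose title refers to the primary efficacy analyses, deals with the 78 of 278 patients who may drop out: "If there is no evidence of informative missing data, analyses will be done using the repeated measures ANCOVA with a mixed models approach". Section 12.5 reuses the repeated-measures form for the secondary outcomes, with 12- and 18-month data added for the cognitive and patient-reported outcomes.

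Sections 12.3 to 12.5 specify no visit term, treatment-by-visit term or 24–27 month contrast for this model. Interactions are named elsewhere: treatment by 6-month change for Aim 2, and treatment by baseline covariates.

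**The concern.** A repeated-measures model with one treatment coefficient assumes the same effect at 6 months and at 24–27 months. If the effects differ, the coefficient estimates neither of them. A benefit that has faded by 24 months could then be reported as preservation at 24 months, and a benefit that emerges late could be missed.

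The plan gives reason to expect a difference. Section 12.3 cites pilot data that injury, and its attenuation by statins, come early, and Aim 2 asks whether the early change predicts the late one.

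The route to Aim 1 is also a planned one. An ANCOVA on observed 24–27 month values cannot include patients without that scan, and the mixed model is the tool that section 12.4 offers for them.

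**Working it through.** **Inputs from the documents.** SD 7.7, baseline correlation 0.5, 100 per arm at 24 months, two-sided alpha 0.05 (section 12.6). There are 278 randomised 1:1 with 200 completing, so (278 − 200)/2 = 39 lost per arm (sections 5.2, 12.1 and 12.4).

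**Assumptions not in the documents.** All pairwise LVEF correlations are 0.5, so the 6- and 24-month values given baseline correlate at ρ = (0.5 − 0.25)/(1 − 0.25) = 1/3. Variances are equal at the two visits. The number m of dropouts per arm with a 6-month scan lies between 0 and 39. The covariance is treated as known.

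**The plan's own figure.** 7.7 × √(2 × 0.75) × (1.96 + 0.842)/√100 = 2.64, as in the section 12.6 table. Power at 2.64 with 100 per arm is 79.9%, and 200/(1 − 0.28) = 278. All reproduce.

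**Model as listed.** Residual variance v = 7.7² × 0.75 = 44.47. With n = 100 per arm seen at both visits, the information per arm on a common effect (in units of 1/v) is n/(1 + ρ) + m = 75 + m from month 6 and n/(1 + ρ) = 75 from month 24. Hence:

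- 6-month weight = (75 + m)/(150 + m)
- SE = √(2v/(150 + m))

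For m = 0 the weight is 75/150 = 0.50 and SE = √(88.94/150) = 0.770. For m = 39 the weight is 114/189 = 0.603 and SE = √(88.94/189) = 0.686.

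**Model with treatment-by-visit, read at 24 months.** The 6-month effect has weight 0. For m = 0, SE = √(88.94/100) = 0.943. For m = 39 the per-arm information matrix is [[151.5, −37.5], [−37.5, 112.5]]/v, so SE = √(88.94 × 151.5/(151.5 × 112.5 − 37.5²)) = 0.928.

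**Rejection rates**, from Φ(δ/SE − 1.96) + Φ(−δ/SE − 1.96), where δ is the expected estimate:

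| True effect at 6, 24 months | m per arm | Expected estimate, as listed | Rejects, as listed | Rejects, 24-month contrast |
|---|---|---|---|---|
| 2.64, 0 | 0 | 1.32 | 40% | 5% |
| 2.64, 0 | 20 | 1.48 | 53% | 5% |
| 2.64, 0 | 39 | 1.59 | 64% | 5% |
| 2.5, 0 | 0 | 1.25 | 37% | 5% |
| 2.5, 0 | 39 | 1.51 | 59% | 5% |
| 2.64, 1.32 | 39 | 2.12 | 87% | 30% |
| 0, 2.64 | 0 | 1.32 | 40% | 80% |
| 0, 2.64 | 39 | 1.05 | 33% | 81% |
| 2.64, 2.64 | 0 | 2.64 | 93% | 80% |
| 2.64, 2.64 | 39 | 2.64 | 97% | 81% |

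The 2.5 rows use the 6-month difference that section 12.6 quotes from preliminary data.

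**Sensitivity.**
- With m = 39, the 6-month weight is 0.595 to 0.624 for ρ from 0.2 to 0.7.
- Adding a visit main effect alone leaves the weights unchanged.
- Unstructured covariance does not remove the averaging. If the 24-month SD is 0.7 to 1.4 times the 6-month SD (an assumed range), the 6-month weight runs from 0.36 to 0.80.
- Section 12.6 expects more power from the mixed model. At ρ = 1/3 the large gain (97% with m = 39) belongs to the averaged effect; for the 24-month contrast power moves only from 79.9% to 81.2%.

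**The case against.** The strongest reply is that the primary analysis is not this model. The ANCOVA in section 12.3 targets the right time point, is said to address Aim 1, and is the basis for power in section 12.6. The repeated-measures model is listed among the additional analyses. All of this stands. A reader might infer that the averaged coefficient is the trial's primary result, but the documents do not establish that: section 12.4 says that analyses will use the mixed model and never says that it replaces the ANCOVA. They do not rule it out either, so which model supplies the Aim 1 result under dropout is itself unsettled.

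Second, a reader might infer that the plan excludes a treatment-by-visit term. It does not; it leaves the term unspecified. The sentence on fixed effects is garbled and may not be a complete list. Section 3.1.1 says that exact time between visits can be accounted for, which hints at some time term. But a time main effect would not separate the two treatment effects, and no interaction with time is mentioned.

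Third, compound symmetry might be blamed. The plan will also examine an unstructured form, and the averaging occurs under either.

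Fourth, the 64% figure is an upper-end case. It needs every dropout to have had a 6-month scan, which sections 7.2 and 7.7 allow to be missed, and a 24-month effect of exactly zero. Early injury does not imply that protection fades: study drug continues to 24–27 months, and sustained equal effects would give an unbiased estimate with 93% to 97% power. That is why a range and the equal-effects case are shown.

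**Conclusion.** The concern holds as an under-specified model on a route that can reach Aim 1. Fitted with the listed terms, the mixed model puts weight 0.50 to about 0.60 on the 6-month effect. A benefit of 2.64 points at 6 months that is gone by 24 months would be called significant in about 40% to 64% of trials, against 5%. A benefit of 2.64 points present only at 24 months would be detected with about 33% power if all dropouts were scanned at 6 months, against 81%.

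These figures rest on residual correlation 1/3, equal variances and the stated range of dropouts with a 6-month scan. There is no bias if the effects are equal at both visits. The primary ANCOVA and the sample size are unaffected.

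Severity: should be fixed. It becomes a must-fix if section 12.4 is meant to replace the primary ANCOVA.

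**What to change.** 1. In section 12.3, write the repeated-measures model with treatment, categorical visit, treatment-by-visit, baseline LVEF and the randomisation strata. Baseline-by-visit and an unstructured covariance are preferable, but the treatment-by-visit term is what removes the averaging.
2. State that this model's Aim 1 estimate is the treatment contrast at 24–27 months.
3. State whether the ANCOVA in section 12.3 or the mixed model in section 12.4 gives the primary Aim 1 result, and make the other one supportive.
4. Use the same form for the secondary outcomes in section 12.5, including those with 12- and 18-month data.

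The cost is a few sentences of analysis-plan text and a few model terms. No new data are needed, and power for the 24-month contrast at 2.64 points is 79.9% to 81.2% under the assumptions above, against the planned 80%.
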